### 9.3 Analysis Datasets

We will compare study endpoints and safety outcomes between the 40 patients who received HBOT treatment with a matched comparison group of 120 patients who received standard treatment. Matching will be based on age, gender, comorbidity, and disease severity. The eligibility criteria for the SOC group will be consistent with that of the HBOT group.

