Description of Study Agent/Procedure	
Hyperbaric oxygen therapy involves placing patients in an enclosed chamber with 100% inhaled oxygen at an increased atmospheric pressure. HBOT chambers have shown efficacy and been cleared by the FDA for 13 conditions:
 
 
• Air or gas embolism
 
• Carbon monoxide poisoning
 
• Clostridial myositis and myonecrosis (gas gangrene)
 
• Crush injury, compartment syndrome, and other acute traumatic ischemias
 
• Decompression sickness
 
• Enhancement of healing in conditions including:                     
 
◦ Diabetically derived illness, such as diabetic foot, diabetic retinopathy, diabetic nephropathy
 
◦ Exceptional blood loss (anemia)
 
◦ Intracranial abscess
 
◦ Necrotizing soft tissue infections (necrotizing fasciitis)
 
◦ Osteomyelitis (refractory)
 
◦ Delayed radiation injury (soft tissue and bony necrosis)
 
◦ Skin grafts and flaps (compromised)
 
◦ Thermal burns
 
 
 

Reference Therapy	
Standard of care matched cohort of patients that did not receive HBOT based on age and gender and if possible underlying medical comorbidities and initial disease severity.

Key Procedures	
 
• Hyperbaric Oxygen Treatment
 
• Review of standard of care pre and post treatment blood draws to evaluate the blood oximetry along with markers of inflammation (e.g., D-dimer, Lymphocytes, IL-6, Ferritin, LDH, CRP, ESR, Fibrinogen, and troponin)
 
• Chart review
 

Statistical Analysis	
For binary primary and secondary endpoints, chi-squared analysis of proportions between the two matched groups with multivariate logistic regression if we find identifiable differences in the two study arms. T-test and linear regression for secondary endpoints that are continuous variables.

CONFIDENTIAL

This material is the property of the NYU School of Medicine and Langone Medical Center. Do not disclose or use except as authorized in writing by the study sponsor

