## **4 Study Design and Endpoints**

### **4.1 Description of Study Design**

This is a multi-center prospective pilot cohort study to evaluate the safety and efficacy of hyperbaric oxygen therapy (HBOT) as an emergency investigational device for treating patients with a novel coronavirus, disease, COVID-19. Patients that meet inclusion criteria will be consented by the hyperbaric physician. They will then be transported from the ED or other unit to the hyperbaric unit maintaining airborne precautions based on the most current hospital protocol. All study personnel will have proper PPE at all times. The patient will then be placed into the monoplace chamber and when the chamber door is closed the patient will remove any respiratory filter/mask that was placed. The patient will receive 90 minutes of hyperbaric oxygen at 2.0 ATA with or without airbreaks per the hyperbaric physician. Upon completion of the treatment the patient will then return to the medical unit and continue all standard of care. Additional treatments (up to 5 total) can be given if warranted and agreed upon by the patient and all members of the team caring for the patient. An interim analysis after the 1st 10 patients will be conducted for all endpoints. During the interim analysis of the first 10 patients and after the intervention portion of this study, a chart review will be performed to compare the outcomes of intervention patients versus age and gender matched control patients who received standard of care.

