### 5.2 Exclusion Criteria

An individual who meets any of the following criteria will be excluded from participation in this study:

1. Pregnancy
2. Untreated Pneumothorax
3. Intubated patients
4. Patients on IV drips

Other conditions are all relative contraindications that need to be discussed with the treating physician and the hyperbaric medicine physician.

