### 5.4 Strategies for Recruitment and Retention

This study will be targeting patients that have tested positive for the novel coronavirus, disease, COVID-19 in the emergency department or other in-patient unit. Patients that meet inclusion criteria will be consented by the hyperbaric physician prior to the first treatment. Study subjects will be transported from the ED or other unit to the hyperbaric unit maintaining airborne precautions based on the most current hospital protocol.

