## **7.3 *Study Schedule***

### **7.3.1 *Screening***

#### **Screening/Enrollment Visit (Day 1)**

- Obtain informed consent of potential participant verified by signature on written informed consent for screening form.
- Review medical history to determine eligibility based on inclusion/exclusion criteria.
- Review medications history to determine eligibility based on inclusion/exclusion criteria.
- Review standard of care test results (e.g. blood oximetry) to determine eligibility based on inclusion/exclusion criteria.
- Schedule hyperbaric oxygen treatment for participants who are eligible and available for the duration of the study.
- Women of childbearing potential age must have a negative serum or urine pregnancy test prior to initial HBO treatment.

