#### 9.4.2 Analysis of the Primary Efficacy Endpoint(s)

The primary endpoint will be patient mortality, a binary outcome variable indicating whether a patient died during hospitalization for COVID treatment. We will compute proportion of patients who died in each

CONFIDENTIAL

This material is the property of the NYU School of Medicine and Langone Medical Center. Do not disclose or use except as authorized in writing by the study sponsor

matched group. Chi-squared test will be utilized to compare rates of incident mortality in each group. We will also report estimates of difference in proportions along with an estimate of uncertainty using 95% confidence interval.

As a follow-up analysis, we will use a multivariable logistic regression, adjusting for any baseline covariates determined to be confounder, to estimate odds-ratio of probability of mortality between HBOT group and SOC group. We will also report 95% confidence interval of the odds-ratio.

Sample size consideration: Using a sample of 160 patients, 40 in HBOT arm and 120 in SOC arm (post matching) we can detect a reduction of 22.5% with 80% power at significance level of 0.05, assuming that the proportion of mechanical ventilation needed in SOC arm is about 80%.

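### Section 9.3 gives chart-review controls no index time, while HBOT patients must be alive and un-intubated at entry; the death and ventilation contrasts can be biased, by an amount and in a direction the documents do not fix

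*Combined protocol and SAP*

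**What the plan says.** Section 9.3 makes the comparison "between the 40 patients who received HBOT treatment with a matched comparison group of 120 patients who received standard treatment". It matches on age, gender, comorbidity and disease severity, and adds that "The eligibility criteria for the SOC group will be consistent with that of the HBOT group". The summary's Reference Therapy row is weaker: age and gender, then "if possible underlying medical comorbidities and initial disease severity". The Brief Summary and section 4.1 name only age and gender.

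HBOT patients enter at a definite point. Section 5.2 excludes "Intubated patients". Section 5.4 recruits "in the emergency department or other in-patient unit" and places consent before the first treatment. Section 7.3.1 puts consent, eligibility review and scheduling on Day 1, and 4.1 describes what follows consent: "They will then be transported from the ED or other unit to the hyperbaric unit".

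The outcome windows are worded alike for both groups. Section 9.4.2 counts "whether a patient died during hospitalization for COVID treatment", and 9.4.3 counts ventilation during treatment. Neither gives a start time. Section 9.4.1 adjusts for baseline variables that differ between the groups. Section 9.1 leaves the formal SAP to the end of the study, and 9.4.7 uses 30 matched controls when the first 10 HBOT patients have completed.

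**The concern.** The asymmetry is in who can belong to each group. A patient who qualifies on arrival, then dies or is intubated before consent, cannot enter the HBOT group. The same course in a control chart satisfies every stated rule and contributes an event. In the other direction, a patient who improves or goes home before consent cannot enter the HBOT group but can be an event-free control.

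The rules that might close this gap do not. Consistent eligibility carries the intubation exclusion over to controls without saying when it is applied. Severity matching does not require a control to be event-free at a matched elapsed time. Covariate adjustment cannot remove events that only one group could contribute, and baseline has no stated time in the control charts.

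At stake are the primary endpoint (death) and the first secondary endpoint (ventilation). A difference can arise without any treatment effect, so the 5% test in 9.4.1 need not hold its level.

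**Working it through.** **Inputs from the documents.** Groups of 40 and 120 (5.7, 9.3); two-sided 0.05 (9.4.1); chi-squared test (9.4.2, 9.4.3); SOC rate 80%, attached to ventilation in 9.4.2 and to mortality in 9.5, where the ventilation calculation is said to be similar; design difference 22.5 points (9.5).

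**The plan's own figure.** For 80% against 57.5%, the pooled proportion is (40×0.575 + 120×0.80)/160 = 0.744. The standard error is 0.0797 under the null and 0.0863 under the alternative. Power = Φ[(0.225 − 1.96×0.0797)/0.0863] = 78.7%, against the stated 80%. The figure reproduces, reading 22.5% as an absolute difference.

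**Assumed inputs.** The documents give no time from first qualifying to consent, so the following are assumptions:
- F: share of SOC patients with an early event (intubation; for the death endpoint, intubation or death) before entry could have happened.
- R: share recovering early.
- c: in-hospital mortality among those with an early event.
- p: SOC event rate. 80% is the plan's; 50% is an assumed alternative.

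**Formulas, with no treatment effect.** If controls are counted from first qualifying and HBOT patients are those who reach entry, then:
- Ventilation: p = F + (1 − F − R)h, so the HBOT rate is h = (p − F)/(1 − F − R).
- Death, R = 0: p = Fc + (1 − F)h, so h = (p − Fc)/(1 − F).

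Examples at p = 0.80: ventilation with F = 0.20 gives h = 0.60/0.80 = 0.750. Death with F = 0.20 and c = 0.9 gives h = 0.62/0.80 = 0.775.

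**Rejection rates.** These come from exact enumeration of two independent binomials (40, 120) and Pearson chi-squared at 0.05. Continuity-corrected values are in brackets, because the plan does not say which form applies.

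| Endpoint, p | F | R | HBOT rate | False reduction (points) | Rejection |
|---|---|---|---|---|---|
| Either, 80% | 0 | 0 | 0.800 | 0 | 5.0% (3.0%) |
| Death, 80%, c = 0.9 | 10% | 0 | 0.789 | 1.1 | 5.6% (3.4%) |
| Death, 80%, c = 0.9 | 20% | 0 | 0.775 | 2.5 | 7.0% (4.5%) |
| Ventilation, 80% | 5% | 0 | 0.789 | 1.1 | 5.5% (3.4%) |
| Ventilation, 80% | 10% | 0 | 0.778 | 2.2 | 6.7% (4.2%) |
| Ventilation, 80% | 20% | 0 | 0.750 | 5.0 | 11.6% (7.9%) |
| Ventilation, 80% | 20% | 5% | 0.800 | 0 | 5.0% (3.0%) |
| Ventilation, 50% | 10% | 0 | 0.444 | 5.6 | 9.2% (6.4%) |
| Ventilation, 50% | 20% | 0 | 0.375 | 12.5 | 27.5% (21.7%) |

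**Sign.** The ventilation bias is zero when R = F(1 − p)/p, which is F/4 at 80% and F at 50%. With F = 10% and R = 5%, the bias is 2.4 points against HBOT at 80% (h = 0.70/0.85 = 0.824) and 2.9 points for HBOT at 50% (h = 0.40/0.85 = 0.471).

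**The case against.** The plan does more than a quick reading suggests. Consistent eligibility rules out controls already intubated when they meet the criteria, and 9.3 itself matches on comorbidity and severity without the summary's qualification. Consent, eligibility review and scheduling all fall on Day 1 and transport follows, so little of any gap can lie between consent and the first session. At the plan's own 80% rate the illustrated bias in death is at most 2.5 points, against a design difference of 22.5. The continuity-corrected rejection rates for death stay below 5%. The study is also a non-randomised pilot with referral by physicians, so aligning the clock would not by itself restore the nominal level.

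Most of this stands, and it limits the weight of the point. It does not close the gap, because none of these provisions says when a control is eligible or requires it to be event-free at the matched elapsed time. The open interval runs from first qualifying to consent.

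A reader might infer three stronger things that the documents do not support:
- That the comparison is rigged towards HBOT. Early recoveries push the other way, and the net sign is unknown.
- That false-positive rates near 27% are to be expected. That figure needs an assumed 50% ventilation rate and a 20% early-event share with no early recoveries.
- That the two groups have different outcome windows. Sections 9.4.2 and 9.4.3 word them alike; the difference is in membership.

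**Conclusion.** The point holds as an inexpensive improvement, with medium confidence. Followed as written, 9.3 allows early events and early recoveries to count in one group only, and no other section prevents it.

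At the plan's 80% rate the illustrated effect is small for death and small to moderate for ventilation. It would be larger, for the same early-event shares, if the true event rate were well below 80%. All sizes rest on assumed F, R and c, on no true effect, and on treating the 160 patients as independent. The death figures also depend on early-event patients dying more often than average: at c = 80% that bias is zero, since (0.80 − 0.08)/0.90 = 0.80.

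A reader might also infer that the HBOT group should be redefined as everyone who consented. The documents do not require that. They define the group by receipt of treatment, leaving only consented-but-untreated patients and aborted sessions (5.8) unresolved. A sensitivity analysis is enough for those.

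**What to change.** Add the following to 9.3 before the 10-patient interim selects the first 30 controls:

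1. Each HBOT patient's index time is entry, meaning Day 1 consent.
2. Its three controls are drawn from SOC patients who are alive, un-intubated, in hospital and eligible at the same elapsed time since first meeting the SpO2 criterion (risk-set matching).
3. Severity and baseline covariates are taken at that time, and death and ventilation are counted from it in both groups.
4. If controls must never have received HBOT (summary, 4.2.2), report how many candidates that rule removed.
5. Report consented-but-untreated patients, with an all-consented analysis as a sensitivity analysis only.

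The SpO2 and exclusion wording of the summary must be reconciled with 5.1 and 5.2, because one definition has to start the clock. This review takes no position on which is right.

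**Cost.** No extra HBOT patients are needed. Time-stamped SpO2, intubation and vital status must be abstracted for a candidate pool larger than 120, and SpO2 is available only where it was charted in routine care (7.1.2). Section 5.5 describes the SOC data as deidentified, so access to dates must be covered by the waiver still to be requested (5.7) and by each of the 11 sites' IRBs. Some candidate controls will be lost, although 9.6.1 expects a very high patient volume. Selection by referral (5.5) and by consent remains and should be stated as a limitation.

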## **5.7 Total Number of Participants and Sites**

There are a total number of 11 sites. All sites will submit their own individual IRB proposal to be approved by their respective institution's IRB. NYU is the lead site and the Co-Principal Investigators, [name] and [name], will be the lead coordinators of this study.

Recruitment will end when approximately 40 participants are enrolled in the HBOT group.

We will create a comparison cohort from chart review of 120 patients who received standard treatment and were matched with 40 HBOT patients in 3:1 ratio, such that the comparison group will consist of 120 standard of care patients. For this retrospective comparison group, we will be requesting a waiver of consent and authorization for this cohort.

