## **5.8 Participant Withdrawal or Termination**

### **Reasons for Withdrawal or Termination**

Participants are free to withdraw from participation in the study at any time upon request. An investigator may terminate participation in the study if:

- Any clinical adverse event (AE), laboratory abnormality, or other medical condition or situation occurs such that continued participation in the study would not be in the best interest of the participant
- The participant meets an exclusion criterion (either newly developed or not previously recognized) that precludes further study participation
- The patient does not tolerate increased pressure in the HBOT chamber
- Study early termination

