### 9.4 Description of Statistical Methods

#### 9.4.1 General Approach

We will summarize the continuous variables using mean, median, standard deviation and ranges, and the categorical variables using frequency and proportions. Variables will also be summarized graphically. Baseline characteristics of the participants who received HBOT will be compared with that of control patients receiving SOC. If we find any significant difference in the baseline variables between the two matched groups, we will adjust for them as covariates in outcome analysis. T-test or ANOVA will be used for continuous variables whereas chi-squared test will be used for comparison of proportions. All tests will be two tailed at significance level of 0.05. Appropriate transformations (such as log transformation) will be considered for any continuous variable that indicates non-normality. Statistical software R and SAS will be used for the analysis.

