### **9.5 Sample Size**

Using a sample of 160 patients, 40 in HBOT arm and 120 in SOC arm (post matching) we can detect a reduction of 22.5% or higher, against the null of no difference, with 80% power at significance level of 0.05, assuming that the mortality rate in SOC arm is about 80%.

For the secondary analysis, our proposed sample of 160 patients will similarly allow us to detect a difference of 22.5% in need for ventilation between HBOT group and SOC group with 80% power. For comparing the continuous outcome of number of days in ventilation, we have 80% power to detect effect size (cohen's d) of 0.51 with 160 patients.

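### Recruitment stops at about 40 enrolled, but the only analysis set is the 40 who received HBOT, so patients enrolled and never treated have no place in the HBOT arm

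*Combined protocol and SAP*

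**What the plan says.** Two sections give the number 40 to groups defined in different ways.

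- Section 5.7 sets the stopping point for accrual: "Recruitment will end when approximately 40 participants are enrolled in the HBOT group". It then describes the controls as "matched with 40 HBOT patients in 3:1 ratio".
- Section 9.3 defines the only comparison, "between the 40 patients who received HBOT treatment with a matched comparison group of 120 patients who received standard treatment". Section 9.4.1 likewise describes the HBOT group at baseline by receipt of treatment.

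Consent precedes the first treatment (Section 5.4). Eligibility review and scheduling (7.3.1) and transport to the hyperbaric unit (4.1) lie between consent and the first session. Section 5.8 allows withdrawal at any time. It also allows the investigator to end participation for a newly developed exclusion criterion, or where "The patient does not tolerate increased pressure in the HBOT chamber". Section 5.2 lists intubation as an exclusion. Section 5.9 continues follow-up of withdrawn and terminated participants, including for efficacy, but for those who withdraw consent it requires vital status only on the day of discontinuation.

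The plan gives no as-enrolled set, minimum exposure, replacement rule or allowance for loss. Adherence and retention analysis (9.4.5) is marked not applicable. Section 9.1 leaves the formal SAP to the end of this unblinded study.

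**The concern.** The two groups of 40 coincide only if every enrolled patient is treated. Anyone enrolled and never treated is outside the set that Section 9.3 names, and this can happen only in the prospective arm, because a chart-review control has no interval between consent and treatment to survive.

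The clearest case is intubation before the first session. The patient now meets an exclusion criterion and may be terminated. Invasive ventilation is also a secondary endpoint. The event can therefore remove the patient from the HBOT arm, whereas the same event in an SOC chart counts against SOC. If untreated patients fare worse than treated ones, HBOT mortality and ventilation are both understated. A smaller loss is precision, since the analysed group could be below the 40 used in the power statement. With the SAP written last and without blinding, who counts as treated could be settled with outcomes known.

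**Working it through.** **Inputs from the plan.** 40 HBOT and 120 SOC, 3:1 (5.7, 9.3). "All tests will be two tailed at significance level of 0.05" (9.4.1). Section 9.5 states "we can detect a reduction of 22.5% or higher, against the null of no difference", and does so "with 80% power at significance level of 0.05, assuming that the mortality rate in SOC arm is about 80"%. Hence SOC mortality is 0.80 and HBOT mortality 0.80 − 0.225 = 0.575.

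**Assumed, because the plan gives no figure.** Untreated share of 10% (4 of 40) to 20% (8 of 40), and mortality in the untreated of 60% to 100%.

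**1. The plan's own power.** Power = Φ[(Δ − 1.96·SE₀)/SE₁], with SE₀ from the pooled proportion and SE₁ from the separate proportions.

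- Pooled proportion = (40×0.575 + 120×0.80)/160 = 0.7438
- SE₀ = √[0.7438×0.2562×(1/40 + 1/120)] = 0.0797
- SE₁ = √[0.575×0.425/40 + 0.80×0.20/120] = 0.0863
- Power = Φ[(0.225 − 0.1562)/0.0863] = Φ(0.797) = 78.7%

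The exact power of the uncorrected chi-squared test is 79.2%. The stated 80% is reproduced within rounding, reading 22.5% as percentage points.

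**2. Power if 4 of 40 are left out.**

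- 36 v 108: Φ[(0.225 − 1.96×0.0840)/0.0909] = 74.6%
- 36 v 120 (all controls kept): Φ[(0.225 − 1.96×0.0825)/0.0901] = 75.9%

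At 20% untreated the figures are 69.9% (32 v 96) and 72.6% (32 v 120).

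**3. Bias if HBOT works as the plan assumes.** Of 40 enrolled, 0.575×40 = 23 die. With 4 untreated who die with probability q, treated-only mortality = (23 − 4q)/36.

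- q = 0.60: 20.6/36 = 57.2%, which is 0.3 points too low
- q = 0.90: 19.4/36 = 53.9%, which is 3.6 points too low

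**4. Bias if HBOT does nothing.** Of 40 enrolled, 0.80×40 = 32 die. Type I error is the exact rejection probability of the two-sided chi-squared test with 3:1 controls at 80%.

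| Untreated | Mortality in untreated | Treated-only mortality | Spurious benefit | Type I error |
|---|---|---|---|---|
| 4 of 40 | 90% | 28.4/36 = 78.9% | 1.1 points | 5.4% |
| 4 of 40 | 100% | 28/36 = 77.8% | 2.2 points | 6.4% |
| 8 of 40 | 90% | 24.8/32 = 77.5% | 2.5 points | 6.7% |
| 8 of 40 | 100% | 24/32 = 75.0% | 5.0 points | 10.3% |

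With no loss, the exact type I error at 40 v 120 is 5.0%. Section 9.4.2 puts 80% on ventilation in the SOC arm, so the same table serves that endpoint. There the 100% rows hold by definition for patients left untreated because they were intubated.

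**5. Cost of analysing everyone enrolled.** If 10% are untreated and carry SOC risk, the HBOT rate becomes 0.9×0.575 + 0.1×0.80 = 0.5975, the difference 0.2025, and power Φ[(0.2025 − 1.96×0.0791)/0.0857] = 71.0%. At 20% untreated it is 62.1%.

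**The case against.** The strongest reply is that Section 9.3 names a group and states no exclusion. Section 5.9 keeps withdrawn and terminated patients in follow-up for efficacy, and the Protocol Summary speaks of providing HBOT to a cohort of 40, so enrolled may be loose wording for treated. This stands in part. A reader might infer that the plan orders these patients dropped; it does not. It gives them no place, and Section 5.9 secures data without assigning it to an analysis.

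A reader might also infer that every withdrawal is lost. That is wrong. Anyone who stops after a session has received HBOT, and Section 6.1.9 lets a session be shorter than 90 minutes, so even intolerance of pressure need not take a patient out. Only those never treated are clearly affected, although without a minimum exposure an aborted compression is unclear.

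The untreated need not be sicker: the listed side effects include claustrophobia and ear discomfort, which may have little to do with mortality. That also stands, and is why the bias runs from almost nothing upward. Section 9.6.1 expects many eligible charts, so 120 controls could be kept. Finally, analysing as enrolled protects no randomisation here. True, but it stops post-enrolment events from removing patients from one arm only.

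**Conclusion.** The point holds as an undefined analysis population with a one-sided route to bias. The accrual rule counts enrolled patients, the analysis set counts treated patients, both are called 40, and nothing covers the difference.

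Its size depends on an untreated rate that the documents do not give. At 10% untreated and the plan's implied 57.5% mortality, the understatement is about 0.3 to 3.6 points. With no true effect and the untreated all dying, it is 2.2 points at 10% and 5.0 at 20%, with type I error of about 6.4% and 10.3%. The direction favours HBOT only if the untreated do worse.

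Two stronger readings are not supported. The first is that 40 v 120 will not be reached: this needs at least one untreated enrollee, and the accrual target is itself approximate. The second is that the power calculation is wrong: it reproduces from its own inputs, and the loss is about 3 to 4 points if 4 of 40 are untreated.

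**What to change.** - Make the primary analysis set all eligible consented participants, counted in the HBOT arm from enrolment whatever number of sessions they received, including none, each with three SOC matches. Fix eligibility at enrolment, so that a later intubation cannot undo it.
- Keep those with at least one session as a secondary analysis, and define what counts as a session for that purpose.
- Use one term for the 40 in Sections 5.7, 9.3 and 9.5.
- State how in-hospital death is handled for those who withdraw consent. Section 5.9 requires vital status only on the day of discontinuation, Section 7.3.3 stops collection of hospital data on withdrawal of consent, and Section 12.4 allows some data to be discarded.
- Settle this before outcomes are reviewed, not in the end-of-study SAP.

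The cost is mostly wording, plus a missing-outcome rule. The statistical price is dilution: about 71% power for the stated effect if 10% are untreated and carry SOC risk, which is below the 74.6% of the treated-only set. If the sponsor wants 40 treated patients for the secondary analysis, 40/(1 − 0.10) gives 45 enrolled at 10% untreated, and 40/(1 − 0.20) gives 50 at 20%.
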